**Background:**

Stoma formation may be necessary after bowel surgery and involves diversion of the bowel to the skin, where the gut contents are emptied into a bag. Data from Denmark and the UK indicates that, in Northern Europe, 2 000 per 1 million people are presently living with a stoma . In the treatment of rectal cancer, low anterior resection (LAR) with sphincter-preserving surgery following the principles of total mesorectal excision (TME), is the current gold-standard treatment. In cases where the tumour threatens the sphincteric apparatus, an abdomino-perineal excision (APE) is performed. Hartmann's procedure is chosen in a selected group of patients in whom an attempted primary anastomosis is not safe or technically feasible. An APE and many Hartmann's procedures will result in a permanent end colostomy 

The change of anatomy can cause practical difficulties and can cause a feeling of loss of control and changed body image. It is well-established that these changes can reduce the patients' quality of life and have negative impact on daily living. Studies have also shown that living with and the acceptance of a stoma have large cultural, social, religious, and demographic differences. Likewise, how Health Related Quality of Life (HRQoL) is perceived may differ between various populations.

With an increasing population of cancer survivors, there is a need for attention towards the long-term sequela appearing when patients are adjusting to a cancer free life in their own homes. The negative impact on bowel function after surgery for rectal cancer with an anastomosis the LAR-syndrome has been meticulously studied recent years with great benefit for patients specially with the development of the LARS-score. To make the same progress with stoma patients there is a need for a quick and reliable quantification of stoma-bother, identifying the patients with poor functional results in need of further attention and treatment.

Recently, we have developed 'The Colostomy Impact Score' (CI-score), which is a simple scoring system evaluating stoma-problems in patients with a permanent colostomy after rectal cancer surgery. It was based on direct patient-reported individual outcome measures concerned with various aspects of daily life with stoma, as mapped against overall HRQoL. 610 patients treated between 2001-2007, answered a 22-items basic stoma questionnaire and one anchor question addressing the overall stoma impact on HRQoL. Regression analyses identified 7 items/questions with significant impact on HRQoL, and each item/question was allocated a weighed scoring-value. The score comprises 7 items and has a sensitivity of 85,7% for detecting patients with significant impact on HRQoL.

This CI-score is currently available in Danish and English and was developed on a Danish population. We believe it to be a quick and reliable tool to screen patients for stoma-related negative impact on HRQoL. There is no doubt that there are significant cultural, social, religious, and demographic factors that can influence a patient's experience of life with a stoma. In addition to this, perception of an individual's HRQoL is known to differ between various populations [13], [14]. Therefore, before widespread uptake of the CI-score can be promulgated, studies on reliability and validity must be performed internationally across multiple patient populations.

This retrospective cohort study has three main aims: 1) To identify demographic and socioeconomic factors influencing stoma impact and HRQoL, 2) To assess reliability and to validate the translated and cross-cultural adapted CI score internationally in multiple different centres, across a variety of patient groups and across cultural, religious, socioeconomic and physical borders and 3) To investigate if differences in everyday stoma care and -costs across countries and cultures affect CI or HRQoL.

### **International validation of the Colostomy Impact Score**

**Objectives:** To study the influence of diversity in demographic, religious and socioeconomic factors as well as everyday stoma care on CI-score and HRQoL between countries and cultures.

Furthermore, to study the reliability and validity of the CI-score in different countries (Australia, Brazil, China, Denmark, Egypt, Israel, The Netherlands, Lithuania, Portugal, Russia, South Africa, Spain, Sweden, Turkey and the UK) by testing the CI-score against validated measures of quality of life and including test-retest reliability.

#### **Material and methods:**

International validation will be conducted as a retrospective cohort study. Local health care professionals will identify includable patients and register relevant clinical information on each patient from the hospital chart. Most centres will include patients from national or regional databases, some will however include conveniently if a database is not available. Our international collaborators will be responsible for sending out and collecting the questionnaires and returning the completed questionnaires to the undersigned. In countries with sufficient internet accessibility and -infrastructure the data collection will be web based i.e. patients are sent a link to the redcap-database for them to enter their answers directly. Some centres will employ paper versions of the questionnaires. In areas with substantial number of illiterates investigator led interviews can be performed.

**Inclusion criteria:** Patients who were operated with curative intent for rectal cancer with APE, Hartmann's procedure or pelvic exenteration will be included retrospectively aiming at 250 patients from each of the participating countries. This number is based on a calculation of strength based on the results from the development of the CI-score. (mean EORTC score in the major CI-group: 72. SD: 22. Minimal clinical difference: 10 points. Alpha: 0,05 STATA => sample size 206 patients. Expected dropout: 20%). Accessibility to cohorts of interest may differ between countries. Therefore, number of patients and mode of contact to patients should be agreed by the local investigation and the steering group in the planning of the data collection and included as individual amendment to the final protocol. In Denmark patients operated from January 1st 2001 to December 31st 2016 will be included.

**Exclusion criteria:** Age less than 18 years, known disseminated or recurrent disease, mental dementia and the inability to understand the actual language.

As the CI-score is a construct based on a formative model, statistical analysis based on the Classical

Test Theory (CCT) and Item Response Theory (IRT) cannot be applied. However, the following aspects of validity and reliability from the COSMIN checklist can and will be evaluated:

*Content validity:* Comprehensiveness and relevance of the questions in the CI-score have been ensured with the way of the development of the CI-score with the starting point in a Basic Stoma Questionnaire developed by an expert group supplemented by patients ensuring that all possible factors affecting stoma function/impact was included before regression analysis lead to the seven weighed questions. After translation and cross-cultural adaptation face-validity of each translated CI-score will be assessed again by the collaborators before inclusion of patients.

*Construct validity:* This will be tested with hypothesis-testing. The following a priori formulated hypotheses on the construct validity will be tested:

- With a cut-off at 10 point the CI-score will have a sensitivity of at least 85% and a specificity of at least 50% of identifying patients with substantial colostomy impact as measured by the anchor questions (Anchor 1: poor/very poor satisfaction, remaining: Some/major impact).
- Patients with a CI-score of  $\geq 10$  have significant higher scores than patients with CI-score of  $< 10$  on all scales on the EORTC-QLQ-C30 questionnaire and this difference is clinically relevant in global health status, role functioning, social functioning and fatigue.
- Patients with a CI-score of  $\geq 10$  have significant higher scores than patients with CI-score of  $< 10$  on all scales on the EORTC-QLQ-CR29 and this difference is clinically relevant in stoma care problems.
- Patients with a CI-score of  $\geq 10$  have significant worse index value in the EQ-5D-L compared to patients with a CI-score of  $< 10$ . The sensitivity and specificity are expected to be comparable to when comparing to the anchor questions (hypothesis #1).
- The sensitivity and specificity are expected to be the same across all countries performing the validation.
- Men and women have the same relation between CI-score and HRQoL.
- If stoma care products confer a financial burden on the household the CI-score will show poorer correlation with HRQoL compared to patients where stoma care products do not confer a financial burden on the household.
- If the patients' religious affiliation or practice conflicts with having a colostomy, the CI-score will have a poorer correlation to HRQoL compared to patients who are not religious or if their religious practice does not conflict with having a stoma.
- Patients who had their colostomy in the acute setting will have a poorer correlation between CI-score and HRQoL compared to patients operated in an elective setting.
- Patients who postoperatively had serious complication to their surgery (Clavien-Dindo  $\geq$  IIIb) will have a poorer correlation between CI-score and HRQoL compared to patients with no or minor complications.
- The following hypotheses on differences in HRQoL between different groups will be tested:
- Women colostomates have inferior HRQoL than men
- Obese patients ( $BMI \geq 30 \text{ kg/m}^2$ ) have inferior HRQoL than patients with a  $BMI < 30 \text{ kg/m}^2$
- Patients who perform their everyday stoma care themselves have a better HRQoL than patients who require help.
- Patients using irrigation for their stoma care have a better HRQoL than patients who do not irrigate.
- Patients who report the costs for stoma care products confer a burden on their household finances have an inferior HRQoL than patients who do not report this.

- Patients who report having the possibility to see a stoma care nurse if necessary have better HRQoL compared to patients who report not having this possibility.
- Patients who have had surgery in relation to their stoma for any reason have inferior HRQoL than patients who have not have surgery to their colostomy.
- Patients who report having a bulge in relation to their colostomy have inferior HRQoL than patients who do not report having a bulge.
- Patients who believe they have a hernia in relation to their colostomy have inferior HRQoL than patients who do not report having a hernia.

For convergent validation the CI-score will be tested against 5 anchor questions (not validated) and the EORTC QLQ C30+CR29 (validated). Cross-cultural validity: See translation section.

*Reliability:* For a randomly selected subgroup in each country the CI-score and anchor question will be administered twice with an interval of approximately 2 weeks. The two administrations will be independent and both the setting when answering and the forms of administration will be similar for the individual patient. For ensuring stable patients an extra question on recent changes in stoma function will be added to the retest.

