#### Statistical analysis:

Statistical analysis will be performed separately for each country.

The correlations between total CI-score, anchor questions and the EORTC questionnaire results will be calculated for all participating patients according to the guidelines for the scores. For each CI-score group (minor CI/major CI) the mean EORTC QLQ C30-score will be calculated, testing the overall difference of impact on HRQoL between the CI-score groups.

Using the anchor-questions, the patients are divided into two HRQoL groups of those reporting no/minor or some/major impact on HRQoL. Relationship between CI-score and HRQoL group will be illustrated in box-plot for each country, where we expect statistically significant differences in median CI-score between the two HRQoL groups. Differences will be tested by Mann-Whitney U test. A contingency 2 by 2 table will be used to assess the degree of agreement between the two CI-score groups and the two HRQoL groups. Based on this, the sensitivity for the score will be calculated for each country. The added questions about irrigation and stoma-bag change frequency will be compared country-wise. Univariate regression analysis, descriptive analysis and estimation of impact on HRQoL will be performed. Test-retest reliability will be evaluated using Intraclass Correlation Coefficient and Cohens' Kappa.

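### The target of 250 patients per country leaves 200 after the plan's own 20% dropout, 6 fewer than the calculated 206

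*Combined protocol and SAP*

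**What the plan says.** The sample size is given within the inclusion criteria under Material and methods. Patients are to be included retrospectively, "aiming at 250 patients from each of the participating countries". The next sentence gives the basis: "This number is based on a calculation of strength based on the results from the development of the CI-score". The inputs follow in brackets: a mean EORTC score of 72 in the major CI group, an SD of 22, a minimal clinical difference of 10 points, and then "Alpha: 0,05 STATA => sample size 206 patients. Expected dropout: 20" per cent.

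The same paragraph notes that access to cohorts may differ between countries, so that "number of patients and mode of contact to patients should be agreed by the local investigation and the steering group", to be recorded as an individual amendment.

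The Statistical analysis section makes the country the unit of analysis: "Statistical analysis will be performed separately for each country". It also names the comparison that the calculation appears to serve: "For each CI-score group (minor CI/major CI) the mean EORTC QLQ C30-score will be calculated", with a test of the difference between the two groups.

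**The concern.** The paragraph presents 250 as the result of two figures, 206 and 20%, but those figures do not produce it. Dropout is a fraction of the patients who are included, so the required number has to be divided by 0.80. A target of 250 with 20% loss ends below the number that the calculation asked for.

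Since each country is analysed on its own, the per-country number determines the power, and pooling is not the stated remedy. A reader would take the plan to deliver 206 evaluable patients per country when, on its own dropout figure, it expects 200. The reader also cannot tell what 200 delivers, because the power, the sidedness and the split between minor and major CI are not given.

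**Working it through.** **Inputs from the inclusion criteria (Material and methods):** target 250 per country; calculated size 206; dropout 20%; difference 10 points; SD 22; alpha 0.05. **Not stated:** power, sidedness, minor/major CI split, and whether 206 is a total or per group.

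**1. Can 206 be reproduced?** I used a two-sample t-test (noncentral t) with standardised difference 10/22 = 0.4545 and two-sided alpha 0.05. The power and the split were varied in search of 206.

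| Assumed power and split | Solved total | Whole patients |
|---|---|---|
| 90%, equal groups | 205.4 | 103 + 103 = 206 |
| 80%, 25:75 | 204.5 | 52 + 154 = 206 |
| 80%, equal groups | – | 154 |

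At least two sets of assumptions give exactly 206. The documents do not say which was used, if either.

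**2. Total or per group?** If 206 were per group, the target would be 2 × 206 / 0.80 = 412/0.80 = 515, which 250 cannot represent. I therefore read 206 as a total, which is also the reading more favourable to the plan.

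**3. The dropout step.** This does not depend on how 206 was obtained.

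- Expected evaluable: 250 × (1 − 0.20) = 200. Shortfall: 206 − 200 = 6, and 6/206 = 2.9%.
- Included patients needed to keep 206: 206/(1 − 0.20) = 257.5, so 258, which is 8 more than 250.
- Largest loss that 250 can absorb: 1 − 206/250 = 17.6%.
- For comparison, 206 × 1.20 = 247.2, close to 250. Multiplying by 1.20 instead of dividing by 0.80 is a plausible origin, but the plan does not show the step and the finding does not rest on it.

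**4. What the 6 patients cost.** Illustrative, two-sided alpha 0.05, difference 10, SD 22:

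| Split | Power at 206 | Power at 200 |
|---|---|---|
| Equal groups | 90.1% | 89.2% |
| 25:75 | 80.3% (80.5% at 52 + 154) | 79.1% |

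Detectable difference at the assumed power:

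- 90%, equal groups: 9.98 points at 103 + 103, and 10.13 points at 100 + 100.
- 80%, 25:75: 9.93 points at 52 + 154, and 10.11 points at 50 + 150.

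**The case against.** The strongest objection is materiality. Six patients are 2.9% of 206, the cost is about 1 point of power, and a dropout guess is hardly precise enough to separate 17.6% from 20%. No hypothesis or analysis in the plan changes. This stands, and it is why the point is minor.

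Second, 250 is an aim, and the binding number for a country may sit in a local amendment. That limits the consequence but does not correct the stated calculation, and any locally agreed number needs the same dropout step.

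Third, the plan defines neither inclusion nor dropout for a mailed or web questionnaire. If 250 meant completed questionnaires, there would be no shortfall. That reading is possible, but it would leave the 20% with no role in a number said to rest on this calculation. Reading 250 as the number before dropout is the natural one.

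Fourth, the power figures come from searching for inputs that return 206. This is correct: they illustrate the size of the effect and do not recover the original calculation.

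Fifth, the unstated split matters more than the 6 patients. With 206 evaluable, power is 90.1% with equal groups but about 85% at 30:70. This also stands, and it is a reason to state the missing inputs in the same correction.

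**Conclusion.** The concern holds and is minor. On the plan's own figures, 250 per country with 20% dropout yields 200 evaluable patients, not 206; 258 would be needed to keep 206. This rests on two readings: 206 is a total, and 250 is counted before dropout. Both are the natural readings, and the per-group alternative would make the gap far larger.

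The loss is about 1 point of power. Under both reconstructions that give 206, the expected 200 falls just under the assumed power level (90% or 80%), and the detectable difference moves just above the 10-point minimal clinical difference. Confidence is high for the dropout arithmetic; the power values depend on inputs that the documents do not give.

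**What to change.** Keep 250 and restate the sentence along these lines: with 20% expected dropout, about 200 evaluable patients per country are expected, which gives X% power for a 10-point difference (SD 22, alpha 0.05). Compute X from the original STATA run, and state its power target, sidedness and minor/major CI split. X is about 89% if the run was two-sided with equal groups, and about 79% if it was two-sided with a 25:75 split. Say that 206 is a total and that 250 counts patients included before dropout. Where a country amendment sets its own number, divide the required evaluable number by (1 − dropout).

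The cost is one rewritten sentence and a look at the original run; no extra patients are needed. Raising the target to 258 would also repair the sum, at 8 more patients per country, but for about 1 point of power the restatement is enough.

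### Hypotheses 2-4 require significance in each country, but country size has no minimum, so non-significance in a small country may reflect size rather than poor validity

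*Combined protocol and SAP*

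**What the plan says.** **Criterion.** Under construct validity in Material and methods, hypotheses 2 and 3 state that patients at or above the cut-off of 10 "have significant higher scores than patients with CI-score of" below 10, on every scale of the EORTC QLQ-C30 and the CR29 respectively. Both add a second condition, that the difference be clinically relevant. For the C30 this applies to global health status, role functioning, social functioning and fatigue. For the CR29 it applies to stoma care problems. Hypothesis 4 asks for a significantly worse EQ-5D index and names no size of difference. It also expects sensitivity and specificity comparable to hypothesis 1.

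**Unit of analysis.** The Statistical analysis section treats each country on its own. "For each CI-score group (minor CI/major CI) the mean EORTC QLQ C30-score will be calculated", and the groups are then compared. It asks for no confidence interval and gives no rule for reading a non-significant country.

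**Size.** The inclusion criteria aim at 250 per country, derived from "mean EORTC score in the major CI-group: 72. SD: 22", "Minimal clinical difference: 10 points" and "Alpha: 0,05 STATA => sample size 206 patients", plus 20% dropout. Because access to cohorts may differ, the "number of patients and mode of contact to patients should be agreed by the local investigation and the steering group" and recorded as an amendment for that country. No minimum is stated. The Danish entry, beginning "In Denmark patients operated from January 1", runs to the end of 2016 and gives no number. The Background reports that "610 patients treated between 2001-2007, answered a 22-items basic stoma questionnaire" when the score was developed.

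**The concern.** A significance criterion mixes two things: how large the difference is and how many patients were available to show it. If every country had about the planned number, this would matter little. Here the number is settled country by country, for reasons of access, and nothing says how to read a shortfall.

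The study's purpose is to learn whether the score works across cultures. A country that recruits few patients could be reported as not confirming hypotheses 2-4 when its data are compatible with a fully relevant difference. Countries with poor access to cohorts may also be those whose culture or health care differs most from the development setting, so a failure due to size could be taken for a failure due to culture. In the other direction, a large cohort could meet the criterion on differences too small to matter, on those scales where significance alone decides.

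**Working it through.** **Inputs**
- From the inclusion criteria: SD 22, difference 10 points, alpha 0.05, dropout 20%, target 250.
- Assumed, because not stated: two-sided test, equal CI-score groups (30:70 shown as a range), two-sample t-test, and the same SD on every scale. The sample size text does not say which EORTC scale its SD belongs to.
- Illustrative sizes: n=50 and n=100 are not in the documents. n=610 is the number of respondents in the development cohort.

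**Reproducing the plan's figure.** With a standardised difference of 10/22 = 0.455, two-sided 5% and equal groups, the t-test needs 103 per group at 90% power, or 206 in total. This matches the plan exactly (80% power would need 154, 95% would need 254). So 90% power appears to be what was used, although it is not stated. For dropout, 206 x 1.2 = 247, close to 250. Taking 20% off 250 leaves 200 evaluable.

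**Formulas.** For total n in equal groups, SE = 22 x sqrt(4/n) and the 95% CI half-width is t(0.975, n-2) x SE. Power comes from the noncentral t distribution with noncentrality (true difference)/SE. The half-width is also the smallest observed difference that reaches significance.

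| Evaluable n | Half-width, equal groups | Power, true 10, equal groups (30:70) | Power, true 4, equal groups (30:70) |
|---|---|---|---|
| 50 | 12.5 | 35% (30%) | 10% (9%) |
| 100 | 8.7 | 61% (54%) | 15% (13%) |
| 200 | 6.1 | 89% (83%) | 25% (22%) |
| 206 | 6.0 | 90% (85%) | 25% (22%) |
| 610 | 3.5 | over 99.9% (99.9%) | 61% (54%) |

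Example at n=100: SE = 22 x sqrt(0.04) = 4.4, noncentrality 10/4.4 = 2.27, power 61%.

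**Reading the table.** A country of 100 in which the true difference is 10 points misses significance 39% of the time. It has the same 61% chance of passing as a cohort of 610 in which the true difference is 4 points. These are single-scale figures, while hypothesis 2 requires significance on all C30 scales. As a pessimistic illustration, if only the four named scales had to be significant and were independent, the chance would be 0.614^4 = 14% at n=100 and 0.892^4 = 63% at n=200.

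**Hypothesis 4.** The SD of 22 and the 10 points belong to an EORTC score. The documents give neither an SD nor a relevance limit for the EQ-5D index, so the table does not apply. The dependence on n is the same in kind, but its size cannot be computed.

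**The case against.** **Hypotheses 2 and 3 are not judged on significance alone.** This stands. If clinically relevant means 10 points, a 4-point difference fails on the five named scales whatever the cohort size. A reader might infer that Denmark would confirm both hypotheses on trivial differences, and the text does not support that. Two gaps remain: the hypotheses do not tie relevance to 10 points, and the clause does nothing for a small country that fails on significance.

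**Magnitude is already part of the plan.** The Data analysis section does speak of the direction and magnitude of expected correlations, and group means are to be calculated. Neither tells the reader how to treat a non-significant country.

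**The Danish number is unknown.** This stands. A pro rata extension of the development cohort, 610/7 x 16, gives about 1,394. That ignores mortality, and the 2001-2016 window may be a sampling frame under the same aim of 250. Nothing here depends on that figure.

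**The text does not say numbers will fall.** This stands too. It says only that they are to be agreed, in planning, with the steering group. Reduction is a fair inference from limited access being the stated reason. The country amendments are not in the documents and may set adequate sizes.

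**At the planned size the test is adequate.** For a single scale with equal groups, yes: 89-90%. It is therefore not shown that sample size decides the verdict more than the score does. Both matter, and the problem lies in countries well short of the target.

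**Conclusion.** The point holds in limited form. The significance part of hypotheses 2-4 depends on country size, and the protocol sets neither a minimum nor a rule for reading non-significance. On one EORTC scale with a true 10-point difference, the chance of wrongly appearing not to confirm is about 65% at n=50, 39% at n=100 and 10-11% at n=200-206. On C30 and CR29 scales without a relevance clause, a cohort of 610 would reach significance on a 4-point difference 61% of the time.

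These figures rest on SD 22 applied to every scale, equal groups and a two-sided 5% test. A 30:70 split lowers power by roughly 5 to 7 points at n=50-206 for a true 10-point difference. The sizes of 50, 100 and 610 are illustrations. No figure is claimed for the EQ-5D index.

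**What to change.** 1. For every C30 and CR29 scale, report for each country the difference between CI-score groups, taken in the hypothesised direction, with its 95% CI and the evaluable n. A significant but small difference is then visible as such.
2. State that clinically relevant on the five named scales means the 10 points used in the sample size calculation.
3. Count a non-significant result against the score only if the 95% CI lies entirely below 10 points. Otherwise call that country inconclusive on that scale. With a true difference of 10, an interval wholly below 10 arises at most 2.5% of the time at any n, compared with the 39% chance of non-significance at n=100.
4. For hypothesis 4, report the index difference with its 95% CI and do not read non-significance alone as failure.
5. State the power, the sidedness and the assumed split between CI-score groups.

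Two simpler rules should be avoided. Requiring a point estimate of at least 10 is met only about half the time when the true difference is 10, whatever the n. A cut-off at 206 evaluable patients would excuse a country exactly on target, since 250 less 20% is 200.

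The cost is a change of wording and reporting, with no new data. The downside is that some countries will be reported as inconclusive.

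### The Danish validation window covers every treatment year of the Danish development cohort, and the plan has no way to identify or report development respondents; the likely effect is small and limited to Denmark

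*Combined protocol and SAP*

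**What the plan says.** On development, the Background section states: "610 patients treated between 2001-2007, answered a 22-items basic stoma questionnaire and one anchor question addressing the overall stoma impact on HRQoL". It continues: "Regression analyses identified 7 items/questions with significant impact on HRQoL, and each item/question was allocated a weighed scoring-value". It adds that the score "was developed on a Danish population" and "has a sensitivity of 85,7% for detecting patients with significant impact on HRQoL".

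On validation, Objectives lists Denmark among the 15 countries. Material and methods sets the Danish window: "In Denmark patients operated from January 1 st 2001 to December 31 st 2016 will be included". The exclusions are "Age less than 18 years, known disseminated or recurrent disease, mental dementia and the inability to understand the actual language". Country amendments are foreseen, but their described scope is that "number of patients and mode of contact to patients should be agreed by the local investigation and the steering group". Data management and Statistical analysis do not mention earlier participation.

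Numbering the bullets under Construct validity in order, hypothesis 1 asks for sensitivity of at least 85% and specificity of at least 50% at a cut-off of 10. Hypotheses 2-4 compare EORTC and EQ-5D results between the two CI-score groups. Hypothesis 5 expects the same sensitivity and specificity in all countries. Statistical analysis works country by country. It commits to sensitivity per country; specificity appears only in the hypotheses.

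**The concern.** A score tends to perform slightly better in the people whose answers chose its items and weights than in new people, because some of what the regression picked up is particular to those individuals. If they answer again, the part of their response pattern that is stable over time can recur. A Danish sample that mixes development respondents with new patients is then not a clean test of the score.

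The plan allows that mixture and gives no means of seeing it. At stake are the Danish results on hypotheses 1-4, all of which use the derived weights and cut-off, and the hypothesis 5 comparison where Denmark is one of the countries. The hypothesis 1 bar lies 85.7 - 85 = 0.7 points below the development sensitivity, so even a modest optimism is of interest. Once the data are made anonymous for analysis (Ethical considerations), the flag may no longer be recoverable.

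**Working it through.** **1. Do the populations overlap on paper?**

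| | Development (Background) | Danish validation (Material and methods) |
|---|---|---|
| Country | Denmark | Denmark |
| Patients | permanent colostomy after rectal cancer surgery | APE, Hartmann's procedure or pelvic exenteration for rectal cancer |
| Years | 2001-2007 (treated) | 2001-2016 (operated) |
| Number | 610 | target 250 |

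All 7 development years fall within the 16 validation years: 7/16 = 43.75%. The development cohort is 610/250 = 2.44 times the target, so numbers alone do not rule out a large overlap. In 2017 these patients would be 2017 - 2007 = 10 to 2017 - 2001 = 16 years past surgery, so death, recurrence and non-response may make it small. The documents give no overlap figure. Below, 10-44% is an assumed range; 44% is the share of calendar years, not a patient count.

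**2. The plan's own sample size.** With a difference of 10, SD 22, two-sided alpha 0.05 and 90% power (power is not stated), a two-sample t-test needs 103 per group, or 206, as given. Then 206 × 1.20 = 247, close to the target of 250. I use 250 for Denmark, although the protocol lets numbers vary by country.

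**3. Optimism when a development respondent answers again.** The derivation details are not in the documents, so these are illustrative simulations. Both use 610 patients, 22 binary items of which 10 have a true effect, forward selection of 7, integer weights, the highest cut-off with sensitivity of at least 85%, prevalence of 20, 35 or 50%, and reliability of 0.70 or 0.85. Optimism is the result in the same patients minus that in independent patients, on new answers only, in percentage points.

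| Setting | Sensitivity | Specificity |
|---|---|---|
| A: as above | 0.6-1.4 | 0.5-0.8 |
| B: items correlated 0.2, persistent patient effect | 0.19-0.85 | 0.18-0.39 |
| B, anchor not used in derivation | 0.08-0.78 | 0.11-0.47 |

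Effect on the Danish estimate = share × optimism. For sensitivity this runs from 0.10 × 0.08 = 0.01 to 0.44 × 1.4 = 0.62 points; for specificity, from 0.10 × 0.11 = 0.01 to 0.44 × 0.8 = 0.35 points.

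**4. Compared with sampling error.** The half-width for sensitivity is 1.96 × √(0.857 × 0.143/k), with k affected patients. For 250 patients with an assumed 50% or 20% affected, k = 125 gives 6.1 points and k = 50 gives 9.7. For specificity, 1.96 × √(0.25/m) with m = 200 or 125 gives 6.9-8.8 points.

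**5. Effect on the 85% bar.** The documents do not state a decision rule; I assume the point estimate must reach 85%. With k = 125 that means at least 107 detected. The chance of this, without optimism and then with +0.6 points, is:

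- true 80%: 7% to 9%
- true 84.5%: 42% to 50%
- true 85.7%: 57% to 65%
- true 90%: 96% to 98%

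**6. Would agreement between the two analyses show independence?** Take zero optimism, a true sensitivity of 85.7% and k = 125. Let X (participants) and Y (non-participants) be independent binomials. The two conclusions differ when exactly one of (X+Y)/125 and Y/(number of non-participants affected) reaches 85%. With 12 of 125 flagged, this happens 10% of the time; with 55 flagged, 22%. With k = 50 the figures are again 10% and 22%. Disagreement of that size is chance alone.

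**The case against.** The strongest reply is that the effect hardly matters. It concerns one of 15 countries, the simulated optimism is far inside the confidence interval, and the study's central purpose is the translated score elsewhere, while the Danish version is the source. The documents nowhere call the Danish estimate independent. All of this stands, and it makes the point minor. Denmark is nevertheless a named validation country and enters hypothesis 5, so disclosure is reasonable.

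The simulation settings and overlap shares are also assumptions. That stands too: how the cut-off of 10 was chosen, and whether 85.7% was corrected for optimism, are not in the documents. The country amendments are not available either; their described scope does not include earlier participation.

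Two stronger readings are tempting. A reader might infer that the old answers are reused. The documents point the other way: "Our international collaborators will be responsible for sending out and collecting the questionnaires", there are five anchor questions rather than one, the database is still to be built, and collection was to start in the second half of 2017. The issue is the same people answering again.

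A reader might also assume that development respondents would again show 85.7%. With a share of 43.75% and 80% in new patients, the pooled figure would be 0.4375 × 85.7 + 0.5625 × 80 = 82.5%, a rise of 2.5 points. Nothing in the documents supports that assumption: the 85.7% belongs to earlier answers on one anchor, and the simulated gap between the same and new patients is at most 1.4 points.

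**Conclusion.** The point holds as a minor one. By its inclusion rule the plan lets people who helped derive the score also help validate it in Denmark, and it provides no means of reporting how many did. The documents establish eligibility, not actual overlap.

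Any optimism in the Danish estimates is probably under about 1 point: roughly 0-0.6 for sensitivity and 0-0.4 for specificity, given the assumed 10-44% share and the simulation settings above. Only near the 85% bar, and under an assumed point-estimate rule, would this visibly change the chance of meeting hypothesis 1. Other countries' own estimates are untouched, and the study's main conclusions are not threatened.

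**What to change.** Keep the 2001-2016 window and all Danish patients.

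- When patients are identified, and before the data are made anonymous for analysis, flag respondents to the development questionnaire by linkage. If linkage is not possible, ask one question on earlier participation. Report how many there are.
- Give Danish sensitivity and specificity, the Danish comparisons by CI-score group (hypotheses 2-4) and the hypothesis 5 comparison twice, with confidence intervals: for all Danish patients and for non-participants only.
- Describe only the non-participant estimate as independent of the score's development. Do not make that description depend on whether the two analyses agree on the 85% bar: agreement would not make the pooled estimate independent, and disagreement is often chance (step 6).
- If only a split by operation period (2001-2007 versus 2008-2016) can be had, present it as descriptive. In 2017 it compares patients about 10-16 years after surgery with patients about 1-9 years after, so it is confounded with time since surgery.

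The cost is one linkage step or one question, and a short addition to the analysis plan. Linkage may need local approval, and the documents do not say whether development identifiers were kept. Intervals widen in the non-participant analysis only. If 10% of an assumed 250 are flagged, 225 remain and the sensitivity half-width goes from 6.1-9.7 to 6.5-10.2 points. If 44% are flagged, about 141 remain and it is 8.2-12.9 points. Non-participants from 2001-2007 may be a selected group of earlier non-responders. The two analyses serve disclosure; they cannot detect a bias of 0.6 points.
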